All data will be collected on the attached case report form (CRF) and then input by study personnel at each individual site into the University of Miami REDCap electronic data management system. Each site PI will be responsible for keeping a secure file linking the patient medical record number (MRN) to their study ID in the event that additional information is required for study analysis, which will be destroyed at the conclusion of the study. Individual patient MRNs will not be entered into REDCap; the individual subjects will be identified using their study ID. Protected Health Information (PHI) that will be entered into REDCap include hospital admission and discharge dates, ICU admission and discharge dates, date of death (if applicable), and age. The dates entered into REDCap will be used to calculate ICU and hospital lengths of stay, however the exact dates will be removed from the report used for statistical analysis using the feature in REDCap to extract de-identified data only. Data analysis will be performed by [name], PhD (see *Section XII*).

UM IRB No.: 20211211

NCT05545735

Protocol Date: November 14, 2023

Principal Investigator: [name]., M.S.P.H.

Study Title: The Duration of Antibiotic Therapy for Early VAP (DATE) Trial

CRFs will be stored in the Trauma Research Office, located in the Ryder Trauma Center, [name]. Security measures include a locked door to enter [name] and an additional locked door to enter the Trauma Research Office. Across all other sites, measures to ensure compliance and security of protected health information will be subject to the local IRB policies.

The de-identified data report will be used by [name] to perform statistical analyses. No elements of PHI will be included in the file for statistical analysis. The only information sent from our site to [name] for analysis will be what is contained in the de-identified report. Our data will not be shared with any other entity.

The de-identified data from the study will be maintained on the REDCap database for use for future secondary analyses using the trial data. Interested investigators may contact the PI with a request for the de-identified data and access may be granted if an appropriate study design is proposed.

XXVIa. Will the research collect protected health information or personally identifiable information from the EMR or from subjects at UHealth and/or JHS?

Yes

XXVIb. Check the box next to the correct statement below:

Research subjects will sign a HIPAA Authorization before the research will collect this data.

Research subjects will not sign a HIPAA Authorization for this data collection and the research is requesting a waiver of HIPAA Authorization from the IRB.

XXVIc. How will the research store the data?

University of Miami REDCap

UM IRB No.: 20211211

NCT05545735

Protocol Date: November 14, 2023

Principal Investigator: [name]., M.S.P.H.

Study Title: The Duration of Antibiotic Therapy for Early VAP (DATE) Trial

XXVIId. Select one of the following:

The Principal Investigator (and/or Study Team members) will record (e.g., write down, abstract) data acquired in a manner that does not include any indirect or direct identifiers and the recorded data will not be linked to the individuals' identity.

The Principal Investigator (and/or Study Team members) will record (e.g., write down, abstract) the data collected in a manner that does not include any direct identifiers of any subject. Instead, the Principal Investigator and/or Study Team members will assign a code (that is not derived in whole or in part from any direct or indirect identifiers of the individual) to each study subject and link the code to the study subject's identity. The link to each subject's identity and/or other identifiable information will be maintained on a document separate from the research data.

XXVII. Biospecimens

Not applicable. No biospecimens will be collected.

XXVIII. Provisions to Protect the Privacy Interests of Subjects

The research team will access patient health records via daily screening of the electronic health record, as described above. The only contact with the patient and/or legally authorized representative will be to obtain consent for participation in the study. No additional screenings or procedures will be performed as a result of this study, thereby protecting the privacy interests of the subjects.

XXIX. Compensation for Research-related Injury

There is no compensation for research-related injury. We do not anticipate any injury to result directly as a consequence of the proposed research study.

UM IRB No.: 20211211

NCT05545735

Protocol Date: November 14, 2023

Principal Investigator: [name]., M.S.P.H.

Study Title: The Duration of Antibiotic Therapy for Early VAP (DATE) Trial

XXX. Economic Burden to Subjects

Subjects will not be responsible for any additional costs as a result of participation in this research study. Rather, they may experience decreased costs as it relates to less days of antibiotic therapy.

XXXI. Consent Process

We will be obtaining consent for participation in this study as outlined by the SOP: Informed Consent Process for Research (HRP-090). Consent will take place at the patient bedside and/or via telephonic witnessed consent. In the majority of cases, patients will be on the ventilator and sedated, thus not able to participate in the consent process. Therefore, their legally authorized representative will be asked to provide consent. This is the only practical approach as, by nature of the disease process being studied, the patients will generally be unable to participate in the informed consent process themselves. Ongoing consent will be implied unless the patient or their representative requests to be withdrawn from the study. If the patient becomes liberated from the ventilator during the study, and the treating clinical team determines the subject has the capacity for consent, they will then have the ability to re-consent or withdraw consent. Non-English-speaking patients will be eligible to participate as well, and the informed consent process will be conducted using a certified interpreter as provided by the hospital.

REMOTE CONSENTING for a participant's LAR that is unavailable for in-person consenting may include the following:

1. Send a copy of the consent document to the participant's LAR before the discussion.
2. Arrange a video conference meeting or a conference call (if you cannot use Zoom) that includes:
 - a. Person obtaining consent

UM IRB No.: 20211211

NCT05545735

Protocol Date: November 14, 2023

Principal Investigator: [name]., M.S.P.H.

Study Title: The Duration of Antibiotic Therapy for Early VAP (DATE) Trial

- b. Participant's LAR
- c. Additional people requested by the LAR (e.g., relative, friend)
- d. If you are not able to use a video conference system or if the participant will not be able to provide an electronic signature, include an impartial witness
- e. Video conferencing via Zoom for Healthcare will be used for remote consent whenever it is possible.

3. Identify everyone on the call or video conference
4. Confirm the identity of the LAR by viewing their driver's license or another form of identification. If you can confirm the identity visually, document that you recognized the individual. Another alternative is to create and provide a passcode to the potential participant via text or email and ask them for the passcode during the meeting.
5. Review and explain the information in the consent document.
6. Answer any questions the LAR has about the study
7. Ask the LAR questions about the study to confirm their comprehension
8. Ask the LAR if they consent to participate
9. If the LAR agrees, ask them to sign and date the consent document electronically (i.e. REDCap)
10. If you are unable to obtain an electronic signature, ask the LAR to:
 - a. Sign and date the consent document;
 - b. Take a picture of the signed copy of the consent document; and
 - c. Forward the images to you.
11. If there is a witness to the procedure, have the witness sign and date a copy of the document (electronically or with wet ink) and provide a copy of the signed and dated document to you.
12. Sign and date the consent document as the individual obtaining consent
13. Repeat and/or include the same process for HIPAA Authorization

UM IRB No.: 20211211

NCT05545735

Protocol Date: November 14, 2023

Principal Investigator: [name]., M.S.P.H.

Study Title: The Duration of Antibiotic Therapy for Early VAP (DATE) Trial

14. If the LAR signed electronically, explain how they will receive a copy of the signed documents.

Documenting remote consent process:

1. Explain the rationale for obtaining remote consent and HIPAA Authorization
2. Document the date and time you obtained the participant's consent
3. Document the list of attendees by name and role
4. Document whether you obtained consent via a Zoom meeting or phone call
5. Document the electronic platform used to obtain consent (REDCap)
6. Document how you confirmed the participant's identity
7. Document that you answered all of the LAR's questions.
8. Document that you assessed comprehension by asking the participant/LAR questions, and the LAR was able to answer the questions correctly and apparently understood.
9. Document that the LAR verbally agreed to participate or permit the participant to participate.
10. Print the signed and dated copies or images and maintain a copy in the research record and upload to the electronic medical record, if applicable. If you are using an electronic platform as a regulatory binder, transfer the images and documents electronically into the electronic platform and follow requirements for certified copies
11. Document how you provided a copy of the signed and dated consent form and HIPAA authorization to the LAR if you obtained an electronic or wet signature and date. You may use email to send the consent document if you include "SECURE" in the subject line.
12. Document the circumstances if you were unable to obtain a signature and date

Example: Informed consent was obtained on Date at Time. The participant was not able to come to the site because personal reasons. A copy of the consent document was emailed to the

UM IRB No.: 20211211

NCT05545735

Protocol Date: November 14, 2023

Principal Investigator: [name]., M.S.P.H.

Study Title: The Duration of Antibiotic Therapy for Early VAP (DATE) Trial

prospective participant before the consent discussion. REDCap was used for electronic documentation of obtaining consent. The consent process was performed by phone/ZOOM. The individuals attending the discussion were: (list the names of the individuals). The identity of the LAR was confirmed via passcode or viewing their driver's license. The person obtaining consent explained the research to the participant and answered the participant's questions. The person obtaining consent asked the participant questions to ascertain whether the s/he understood the study, and the participant was able to answer the questions. The participant/LAR voluntarily agreed to participate. The subject/LAR signed and dated the consent document. A copy of the signed documents were placed in the research record and another given to the LAR via email. After signing the consent document, the participant took a picture and sent it to the research team/ OR The participant was unable to send a picture of the document because of certain circumstances. An impartial witness observed the entire process.

XXXII. Process to Document Consent in Writing

We will be following "SOP: Written Documentation of Consent (HRP-091)" to obtain written consent and when applicable HRP-093 SOP – Electronic Signatures for Documentation of Consent. Please see the attached informed consent form.

XXXIII. Authorization for Use and Disclosure of Protected Health Information

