Study Title: The Duration of Antibiotic Therapy for Early VAP (DATE) Trial

V. Inclusion and Exclusion Criteria

A) Inclusion Criteria

- a.** Surgical patient
- b.** Early VAP, defined as VAP occurring within 2 – 7 days of intubation (via endotracheal or tracheostomy tube) (9). VAP will be defined according to local institutional protocol.
- c.** Hospital length of stay (LOS) \leq 10 days at the time of VAP diagnosis.
- d.** Patients are willing to provide informed consent or their Legally Authorized Representative (LAR) is willing to provide informed consent on their behalf when the patient is unable (i.e., cognitively impaired from sedation on a ventilator).

B) Exclusion Criteria

- a.** Age $<$ 18 years
- b.** Prior episode of VAP for the index admission
- c.** VAP caused by any of the following pathogens:
 - i.** Methicillin-resistant *Staphylococcus aureus* (MRSA)
 - ii.** Vancomycin-intermediate *Staphylococcus aureus* (VISA)
 - iii.** *Pseudomonas aeruginosa*
 - iv.** Vancomycin-resistant *Enterococcus* (VRE)
 - v.** *Acinetobacter baumanii*
 - vi.** *Stenotrophomonas maltophilia*
 - vii.** Carbapenem-resistant *Enterobacteriaceae* (CRE)
 - viii.** Extended-spectrum beta lactamase-producing gram-negative bacilli
- d.** Causative pathogen not sensitive to choice of initial empiric antibiotic
- e.** Antibiotic therapy for \geq 5 of the last 10 days preceding VAP diagnosis
- f.** Septic shock, defined as evidence of tissue hypoperfusion after adequate volume expansion, due to infection, and requiring \geq 1 vasopressor (17)

UM IRB No.: 20211211

NCT05545735

Protocol Date: November 14, 2023

Principal Investigator: [name]., M.S.P.H.

Study Title: The Duration of Antibiotic Therapy for Early VAP (DATE) Trial

- g.** Current or recent (within 30 days) use of immunosuppressive medications
- h.** LOS \geq 72 hours at a transferring facility
- i.** Pregnancy or lactation
- j.** Legal arrest or incarceration
- k.** Moribund state in which death is imminent
- l.** ECMO (Extracorporeal membrane oxygenation)
- m.** Extubation prior to randomization

VI. Number of Subjects

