The total required sample size for this study is **458 patients**. Assumptions for the power analysis include non-inferiority for VAP recurrence and superiority for antibiotic-free days in the intervention group, 3 planned analyses of the data with O'Brien-Fleming spending function with binding futility boundaries, 25% recurrence rate in the control group (14), and 6 enrolling centers with an average cluster size of 10. To detect a 10% difference in outcomes between groups with 80% power and assuming a 10% dropout rate, a total sample size of 458 patients is required for this study. Sample size will be recalculated at each interim analysis with better estimates based on accrued patients. The planned analyses will take place after enrollment of 150, 300, and all patients.

VII. Study-Wide Recruitment Methods

This is a multicenter randomized controlled trial. We have partnered with the Surgical Infection Society to aid in recruitment of interested centers for participation in the study. The recruitment methods for individual subjects to participate in the study will be uniform across all centers. A member of the research team at each center will screen all patients in their respective surgical ICUs by reviewing the medical record of each patient in the ICU for eligibility based on the inclusion and exclusion criteria listed in *Section V* (above). Screening will occur daily during the study period. We will be requesting a waiver of the requirement for written authorization

UM IRB No.: 20211211

NCT05545735

Protocol Date: November 14, 2023

Principal Investigator: [name]., M.S.P.H.

Study Title: The Duration of Antibiotic Therapy for Early VAP (DATE) Trial

from patients to access their health records due to the nature of the study. Please see further documentation in *Section XXXII* (below).

VIII. Study Timeline

Each individual patient enrolled in the study will be followed for 30 days or until hospital discharge, whichever occurs first. We will also review patient charts at hospital discharge to determine overall hospital length of stay and overall mortality, in addition to 30-day outcomes. We expect all subjects to be enrolled within the first 2 years of study across all centers, with full data analysis completed at 3 months after study completion.

IX. Study Endpoints

A) Primary Outcomes

- a.** VAP recurrence within 30 days
 - i.** VAP recurrence = VAP occurring 2 – 14 days following completion of initial therapy

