- b.** Antibiotic-free days within 30 days

B) Secondary Outcomes

- a.** Antibiotic exposure
 - i.** Days of antibiotics
 - ii.** Antibiotic days (defined as the product of days of antibiotics and number of antibiotics per day)
- b.** Clinical improvement, measured using daily CPIS_{clinical} score while enrolled in the study
- c.** VAP relapse = recurrent VAP caused by initial pathogen (if culture data available), occurring 2 – 14 days following completion of initial therapy
- d.** 30-day Ventilator-free days

UM IRB No.: 20211211

NCT05545735

Protocol Date: November 14, 2023

Principal Investigator: [name]., M.S.P.H.

Study Title: The Duration of Antibiotic Therapy for Early VAP (DATE) Trial

- e. Empyema
- f. Need for tracheostomy
- g. Non-pulmonary infections
- h. 30-day ICU-free days
- i. Hospital LOS
- j. In-hospital Mortality

X. Procedures Involved

This is a multicenter, randomized, clinical trial. The trial will be reported in accordance with the recommendations of the CONSORT statement (18). IRB approval will be obtained. All subjects, or their legally authorized representatives, will provide written consent for study participation. The trial is registered with the US National Institutes of Health (ClinicalTrials.gov Identifier #NCT05545735).

Screening will occur daily by study personnel. Eligible patients will be approached as soon as possible after inclusion criteria are met (i.e., 1 – 3 days prior to randomization). Randomization will occur using a computer-generated block pattern no later than the end of the fourth day of appropriate antibiotic therapy. Randomization will occur at the hospital level in blocks of 20.

Empiric antibiotic therapy will be instituted as soon as possible following diagnosis of suspected pneumonia by the clinical team. The default antibiotic will be based on the local institutional antibiogram and practice. Pre-existing treatment for a non-pulmonary infection with at least one antibiotic that has appropriate activity against the VAP pathogen may be substituted for the default antibiotic. Once sensitivity data become available, therapy may be de-escalated to a more narrow-spectrum agent, as indicated.

The default duration of antibiotic therapy will be determined by study group assignment; the treatment team will be asked to adhere to study group assignment whenever possible. However, the treatment team may choose to extend the duration of antibiotic therapy based on

UM IRB No.: 20211211

NCT05545735

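### Hospital length of stay is counted from admission, so up to about 14 pre-randomization days enter the between-arm comparison and add noise

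*Combined protocol and SAP*

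**What the plan says.** Section IX.B lists hospital LOS as a secondary outcome without saying when the count starts. Two other places show that it starts at admission.

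- Section VIII: study staff will "review patient charts at hospital discharge to determine overall hospital length of stay and overall mortality". The measure is the overall stay.
- The data-confidentiality section, just before XXVIa: the protected data entered into REDCap "include hospital admission and discharge dates, ICU admission and discharge dates, date of death (if applicable), and age". It continues: "The dates entered into REDCap will be used to calculate ICU and hospital lengths of stay". For the file that goes to the statistician, "the exact dates will be removed from the report used for statistical analysis".

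Two rules set how much hospital time can come before randomization. Inclusion criterion c in Section V caps hospital stay at "10 days at the time of VAP diagnosis". Section X lets randomization take place as late as the end of day 4 of appropriate therapy.

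Section IX.B also lists "30-day ICU-free days". No section says how that outcome is derived or which day is day 0.

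**The concern.** The assigned duration of therapy can change only what happens after randomization. If the compared stay starts at admission, each patient's value is the sum of a part that treatment may influence and a part already fixed at randomization. The fixed part varies between patients, so it widens the distribution without contributing to the difference between arms. A real effect of the shorter course on hospital stay, in either direction, becomes harder to detect.

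The dates are removed before analysis. If the count from randomization is not made before export, the statistician cannot rebuild it from the admission and discharge dates.

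**Working it through.** **The plan's own figure.** No effect size, SD or power is stated for any stay outcome, so there is nothing to reproduce for hospital LOS. The total of 458 in Section VI is based on recurrence and antibiotic-free days. It is used here only to fix the number analysed: 458 × 0.90 = 412, or 206 per arm.

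**Step 1: pre-randomization days.** The upper end is 10 days at diagnosis (Section V) plus about 4 days of therapy (Section X), about 14 days. The lower end is taken as about 3 days. This is an assumption. It is consistent with VAP at least 2 days after intubation (Section V) and an approach to the patient or representative at least 1 day before randomization (Section X): 2 + 1 = 3.

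**Step 2: spread of those days (assumption).** If they are evenly spread over 3 to 14 days, SD_pre = (14 − 3)/√12 = 3.2 days.

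**Step 3: variance inflation.** Total stay is pre plus post, so relative to the post-randomization variance

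V = 1 + (SD_pre/SD_post)² + 2ρ(SD_pre/SD_post),

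where ρ is the correlation between the two parts. The SD_post values and ρ are assumptions.

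**Step 4: power.** For each SD_post, take the difference δ that has 80% power at two-sided 0.05 when stay is counted from randomization:

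δ = (1.96 + 0.842) × SD_post × √(2/206).

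Counting from admission leaves δ unchanged and inflates the variance, so

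power = Φ(2.802/√V − 1.96).

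Worked example, SD_post = 8 and ρ = 0: V = 1 + (3.2/8)² = 1.16; 2.802/√1.16 = 2.601; 2.601 − 1.96 = 0.641; power = 74%.

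| SD_post (days) | δ (days) | V, ρ = 0 | Power, ρ = 0 | Power, ρ = +0.3 | Power, ρ = −0.2 |
|---|---|---|---|---|---|
| 8 | 2.21 | 1.16 | 74% | 66% | 80% |
| 10 | 2.76 | 1.10 | 76% | 69% | 81% |
| 15 | 4.14 | 1.05 | 78% | 73% | 82% |
| 20 | 5.52 | 1.03 | 79% | 75% | 82% |

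**Step 5: other spreads.** Over the same four SD_post values, with SD_pre from 2 to 5.5 days (5.5 is the largest SD possible on a 3 to 14 day range), power runs from 79.6% down to 64% at ρ = 0, from 77% down to 53% at ρ = +0.3, and between 73% and 82% at ρ = −0.2.

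**Step 6: rank test on skewed stays.** Section XII plans the Wilcoxon test for non-normal data, and the formula above is a normal approximation. A simulation used 206 per arm, gamma-distributed post-randomization stay with means of 12 and 10 days and SD 8, and independent pre-randomization stay. Wilcoxon power for LOS fell from about 90% to about 81% with pre-randomization stay uniform over 4 to 14 days, and from about 90% to about 86% with 4 to 10 days. This is the short-SD end of the range, where the loss is largest. A skewed distribution can therefore lose somewhat more than the table shows.

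**The case against.** The strongest reply is that little is at stake. Hospital LOS is a secondary outcome with no stated power, and neither primary outcome is touched. Randomization balances the pre-randomization days in expectation, so the comparison is not biased. Overall stay from admission is a familiar and defensible descriptive figure. The power loss rests on SDs, a spread and a correlation that the documents do not give. At an SD of 20 days it is about 1 point, and with a mildly negative correlation it can be nil. All of this stands. It limits the size of the point but does not give a reason to keep days that treatment cannot affect in the between-arm test.

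A reader might also infer that ICU-free days will be computed as 30 minus an ICU length of stay counted from ICU admission, which would charge pre-randomization ICU days against the 30-day window and push patients to zero. The documents do not support this:

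- No section gives that formula, and Section VIII names overall stay separately from the 30-day outcomes.
- The list of dates in the confidentiality section is not presented as complete. It omits timing data that other listed outcomes need, such as antibiotic and ventilator days, and the case report form is not shown.
- REDCap holds ICU dates and date of death, so ICU-free days could be derived before export, given the randomization date.
- The 14-day bound concerns hospital stay. The documents set no corresponding limit on ICU stay before randomization.

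ICU length of stay alone would not yield ICU-free days, but nothing says that it will be used that way.

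**Conclusion.** The point holds for hospital LOS and is minor. As described, the outcome runs from admission to discharge, and up to about 14 days fixed before randomization enter the comparison. The effect is added noise, not bias.

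From a starting power of 80%, the cost is about 1 to 6 percentage points. This assumes 206 per arm, post-randomization SDs of 8 to 20 days, and pre-randomization days spread evenly over about 3 to 14 days and independent of later stay. It is larger if patients with long stays before randomization also stay longer afterwards, and there may be no loss if the correlation is negative. None of these inputs is in the documents, so the figures show a plausible range and are not an estimate for this trial.

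For 30-day ICU-free days, no error and no power loss is shown. The gap there is one of definition: day 0 is not stated.

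**What to change.** For the between-arm comparison, define hospital stay as discharge date minus randomization date. Alternatively, keep total stay and adjust for pre-randomization days. In a linear model with that covariate the treatment estimate is the same whichever starting point is used, because total stay is post-randomization stay plus the covariate. Calculate the day counts in REDCap before the dates are removed, so that the privacy arrangement is unchanged. Report total stay from admission descriptively.

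As a clarification only, state that day 0 for 30-day ICU-free days is randomization, and export the day counts relative to it.

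The cost is one changed REDCap calculation and a sentence in the plan. It presumes that the randomization date is recorded for each patient; the confidentiality section does not list it, but a randomized trial would be expected to hold it. The small downside is that stay from randomization is less directly comparable with reports that count from admission, which is why the total is kept as a descriptive figure.
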